## **Study Design**

This randomized cross-over study measured physiological and perceptual responses of taekwondo athletes following a free combat and combats with different W:R ratios. This study was carried out with 4 visits. The first one included body composition measurements and familiarization to the sessions and measurements. During the rest 3 visit, athletes performed simulated combats free and with 1:2 (10 sec work and 20 sec rest), and 2:1 (20 sec work and 10 sec rest) W:R ratios. During all combat sessions, athletes heart rate (HR), blood lactate (bLA), and counter-movement jump performance (CMJ) were measured at rest and at the end of each combat. HR was also measured following each set. Athletes' rating of perceived exertion (RPE) and perceived muscle soreness (PMS) were measured immediately after each combat.

## **Statistical Analysis**

The data were analysed using SPSS 23 software (SPAA, Inc., Chicago, IL, USA) and JASP software (0.15.0.0 Version, The Netherlands). The Shapiro-Wilk test and descriptive methods using skewness and kurtosis coefficients were used to check for the normality of data. Descriptive statistics and 95% confidence intervals (CI) were used to present subjects' characteristics. Two-way ANOVA with repeated measurements (intervention x time) was used to determine changes in HR (3 x 4), bLA (3 x 2), CMJ (3 x 2) between W:R ratios and measurement times. One-way ANOVA was used to determine changes in PMS. Partial eta squared ( $\eta^2$ ) was calculated to determine the effect size, using the 0.0099, 0.0588, and 0.1379 considered as small, medium, and large effect sizes. In case of significant differences between W:R ratios, paired sample t-test was used, while one-way repeated measures ANOVA was used to determine the difference among measurement times. Cohen's d for paired sample t-test was

automatically provided by JASP software and classified as 0.2 (small), 0.5 (medium) and 0.8 (large). Statistical significance was set at  $p < 0.05$ .

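### The test that decides between W:R ratios is not named: if it is the intervention main effect, rest readings halve a post-combat difference in lactate and jump, and no reading of the plan includes period

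*Combined protocol and SAP*

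**What the plan says.** The Study Design section sets the question: "This randomized cross-over study measured physiological and perceptual responses of taekwondo athletes following a free combat and combats with different W:R ratios". After a familiarization visit, each athlete has three combat visits: "During the rest 3 visit, athletes performed simulated combats free and with 1:2" and 2:1 ratios. HR, bLA and CMJ "were measured at rest and at the end of each combat", and "HR was also measured following each set".

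The Statistical Analysis section gives the model: "Two-way ANOVA with repeated measurements (intervention x time) was used to determine changes in HR (3 x 4), bLA (3 x 2", the quote stopping just before the closing bracket, followed by "CMJ (3 x 2) between W:R ratios and measurement times". The follow-up rule for conditions is "In case of significant differences between W:R ratios, paired sample t-test was used". The time factor has a follow-up rule of its own, given in the same sentence of the plan: "one-way repeated measures ANOVA was used to determine the difference among measurement times".

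The section does not list interaction among the effects that decide, does not give a time point for the paired t-tests, and describes no rest-value covariate, no period or sequence term and no sphericity correction.

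**The concern.** bLA and CMJ have exactly two readings per visit, so the 2 in 3 x 2 must be rest and end of combat. For HR, the 4 in 3 x 4 is most simply rest plus three post-set readings. That is an inference, because the number of sets is not stated.

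A rest reading taken before the combat cannot reflect that visit's W:R ratio. Whether this matters depends on which effect counts as a difference between W:R ratios, and the text allows three readings:

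- **Main effect of intervention.** Rest and post values are averaged, so a post-combat difference is diluted.
- **Intervention x time interaction.** For two time levels this is the test on the change from rest, which is not diluted.
- **Simple effect at each time.** A post-combat t-test is not diluted, but its trigger remains unstated.

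The study asks about responses after combat. Under the first reading a real difference can be missed, and as written the conclusion can depend on which effect is reported. Separately, period is absent from all three readings, so a drift over visits can go into the error term.

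**Working it through.** **Inputs.** From the documents: three conditions, three combat visits, two time levels for bLA and CMJ, four for HR, alpha 0.05. The documents give no number of athletes, SD, correlation, target effect or power, so there is no figure of the plan's own to reproduce and everything else is assumed. The within-athlete, visit-to-visit post-combat SD is 1, the rest SD is k, and their correlation is rho. n = 12. The extreme conditions differ by delta after combat with d_z = 0.8, and the third lies midway. There is no difference at rest. The six visit orders are balanced.

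**Dilution, which needs no assumption about variance.** bLA and CMJ: (0 + delta)/2 = delta/2. HR, if the effect is equal at three post-set readings: (0 + 3 delta)/4 = 0.75 delta.

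**Power for bLA and CMJ.** delta = 0.8 x sqrt(2), so delta^2 = 1.28. The noncentrality of the post-only F-test is n x delta^2/2 = 12 x 0.64 = 7.68 on 2 and 22 df. For the other tests:

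- main effect: 7.68/(1 + k^2 + 2 rho k)
- interaction: 7.68/(1 + k^2 - 2 rho k)
- rest-adjusted, large-sample: 7.68/(1 - rho^2). With athlete, period, condition and covariate fitted, 36 - 12 - 2 - 2 - 1 = 19 residual df remain.

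Example, k = 1 and rho = 0.5: main effect 7.68/3 = 2.56, interaction 7.68/1 = 7.68, adjusted 7.68/0.75 = 10.24.

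Power in %, 20,000 simulated data sets per cell. The first three columns agree with noncentral F within about 0.6 points:

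| k | rho | Main effect | Interaction | Post-only | Adjusted, with period |
|---|---|---|---|---|---|
| 1 | 0 | 35 | 35 | 63 | 60 |
| 1 | 0.3 | 28 | 49 | 63 | 65 |
| 1 | 0.5 | 25 | 64 | 64 | 74 |
| 1 | 0.7 | 22 | 86 | 63 | 89 |
| 0.5 | 0 | 54 | 53 | 64 | 61 |
| 0.5 | 0.3 | 45 | 66 | 64 | 65 |
| 0.5 | 0.5 | 40 | 77 | 63 | 74 |
| 0.5 | 0.7 | 36 | 88 | 64 | 89 |
| 0.25 | 0 | 61 | 61 | 64 | 60 |
| 0.25 | 0.3 | 55 | 68 | 64 | 65 |
| 0.25 | 0.5 | 51 | 73 | 63 | 73 |
| 0.25 | 0.7 | 48 | 79 | 64 | 89 |

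Interaction error variance over adjusted error variance is 1 + (k - rho)^2/(1 - rho^2). It equals 1 at k = rho, where the adjusted model has only its degrees of freedom to lose, and 2 at k = 1, rho = 0.

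**Paired t-test of the extremes** (n = 12, k = 1, rho 0 / 0.5): 43/31% on values averaged over rest and post, 71-72% on post values, 73/84% for the adjusted contrast.

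**Drift over visits** (n = 12, k = 1, rho = 0.5, 0.5 SD per visit, balanced orders):

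- Drift in post-combat values only: main effect 22%, interaction 50% (64% without drift), adjusted model 59% without period and 73% with it. The interaction's type I error falls to about 2%.
- Drift shared equally by rest and post: interaction 62-64% with error 5.0%, because the drift cancels from the change. The adjusted model has 72.0% without period and 73.5% with it.
- Shared drift still hurts the other readings. At n = 18, with a 1 SD period shift (k = 1, rho = 0.5, effect set for about 77% post-only power), the main effect falls from 33 to 19% and post-only from 78 to 67%. The interaction goes from 79 to 78% and the adjusted model with period from 88 to 87%.

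**HR.** The 3 x 4 interaction has (3 - 1)(4 - 1) = 6 numerator df. Power in % at n = 12, with post-set mean d_z = 0.8. GG is the Greenhouse-Geisser interaction over all four times; Adjusted is the post-set mean adjusted for rest, with period:

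| Rest SD; rest-post, post-post correlation | Constant effect: main / GG / Adjusted | Effect growing 1:2:3: GG / Adjusted |
|---|---|---|
| 1; 0.5, 0.5 | 42 / 35 / 82 | 61 / 82 |
| 1; 0.3, 0.8 | 50 / 42 / 65 | 68 / 65 |
| 1; 0.5, 0.8 | 45 / 57 / 76 | 85 / 76 |
| 0.5; 0.3, 0.8 | 57 / 58 / 65 | 87 / 65 |
| 1; AR(1) 0.8 | 42 / 65 / 90 | 86 / 90 |

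Without a sphericity correction, the interaction's type I error is 6.9-8.4% in the last four rows.

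**The case against.** The strongest reply is that the Statistical Analysis section names an intervention x time ANOVA and speaks of changes. Such an ANOVA contains the interaction, and for bLA and CMJ that test uses each visit's rest value through the change score. This stands: on that reading the test is valid, and rest is not ignored merely because it is not a covariate.

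It also stands that the adjusted model is not uniformly better. It trails the interaction by up to about 3.5 points when k is close to rho (74 v 77% at k = rho = 0.5), and the adjusted HR mean loses to the corrected interaction in three of the five growing-effect cases. All sizes rest on assumed inputs. Replacing the ANOVA outright would also drop the planned rest-to-post comparison.

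A reader might go further and infer that the ANOVA is invalid, or that any visit drift costs power whichever effect is tested. The documents support neither: the interaction is sound for bLA and CMJ, and a drift shared by rest and post cancels from it.

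What the reply does not remove is that the text leaves the deciding effect and time point open, that its most literal sense is the diluted main effect, and that a three-period cross-over is analysed without period.

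**Conclusion.** The point holds as one of clarity and power. Three things are firm: rest is a time level for bLA and CMJ, the deciding effect is not named, and period is not modelled. Halving under a main-effect trigger is arithmetic.

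The cost in power is conditional. Over the grid examined, the adjusted model's gain over the main effect runs from -0.5 to +67 points. Against the interaction it is +3 to +24 points at k = 1, but -3.5 to +9 at k = 0.5 or 0.25. Omitting period makes the tests conservative when post-combat values drift. For HR the conclusion is weaker, because the four time levels are inferred and the best summary depends on how the effect develops over sets.

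The documents do not show that the main effect was in fact used, so a reader should not infer that a difference has been missed. Multiplicity of the pairwise tests is a separate matter that this change does not settle.

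**What to change.** **bLA and CMJ.** Compare W:R ratios on the post-combat value in a linear model with athlete, period (order of the three combat visits) and condition as fixed effects and the same visit's rest value as covariate. The 2-df condition effect decides, and pairwise contrasts come from that model. As a check, refit it to the two conditions compared, because pooled contrasts assume equal condition variances (type I error 2.1-6.7% at post SDs 1:1:1.5, against 4.8-5.3% for the two-condition fit).

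**If the ANOVA is kept.** Name the intervention x time interaction as the deciding test for bLA and CMJ. Run the paired t-tests on post-combat values or changes from rest, not on averages over rest and post.

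**HR.** State the four time levels. Take rest out of the time factor, use rest HR as covariate, add period, and analyse intervention and intervention x set over the post-set readings with Greenhouse-Geisser correction. Do not rely on the post-set mean alone.

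**Time.** Keep the planned rest-to-post comparison as a separate analysis.

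**Cost.** No new data are needed. The covariate takes one degree of freedom and period two. If rest and post are uncorrelated and there is no drift, power against post-only falls from 63 to 60% at n = 12 (54 to 49% at n = 10, 84 to 82% at n = 18). The loss against the interaction is up to about 3.5 points when k is close to rho. If visit orders are unbalanced, the period term alone costs about 5 points at n = 12 (74 to 69%). The model also assumes a common rest slope across conditions. Both sections are written in the past tense, so if the data have already been analysed, report this as a revised or sensitivity analysis.

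### Minor: no analysis of this three-visit cross-over includes the visit, a cheap term that may recover power if levels drift; separately, the PMS wording leaves open whether athlete is in the model

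*Combined protocol and SAP*

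**What the plan says.** The Study Design section states: "This randomized cross-over study measured physiological and perceptual responses of taekwondo athletes". It adds: "This study was carried out with 4 visits". Of the first visit it says: "The first one included body composition measurements and familiarization to the sessions and measurements". The other three visits each hold one combat condition: free, 1:2 or 2:1. Apart from calling the study randomised, the document does not say how orders were assigned.

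The Statistical Analysis section lists these inferential analyses:

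- "Two-way ANOVA with repeated measurements (intervention x time", applied to "HR (3 x 4), bLA (3 x 2), CMJ (3 x 2) between W:R ratios and measurement times".
- For the soreness rating given after each session, "One-way ANOVA was used to determine changes in PMS".
- For pairs of conditions, "In case of significant differences between W:R ratios, paired sample t-test was used".
- For times within a condition, "one-way repeated measures ANOVA was used to determine the difference among measurement times".

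None of them has a term for visit, period or sequence.

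**The concern.** Each athlete meets the three conditions on three different days. If levels drift over those days through residual learning, training or fatigue, the drift becomes part of the athlete-by-condition error. That error is the yardstick for the intervention main effect and for the paired comparisons of levels. Random order prevents bias on average but does not remove this noise, and a paired t-test cannot hold a visit term. What is at stake is power. In addition, if the orders came out unequal, part of an observed W:R difference could be a visit effect that the planned analysis cannot show.

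The PMS analysis raises a second, separate question. The same athletes give PMS under all three conditions, yet the plan writes repeated measures for the comparison of times and omits those words for PMS.

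**Working it through.** **Nothing to reproduce.** The plan states no sample size, power, SD or drift. All inputs below other than the design and the 5% level are assumptions: n = 12, one value per athlete and visit, within-athlete SD 1, condition means -0.6, 0 and +0.6, and linear drift of d SD per visit.

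**1. Can time mean visit?** No. The dimensions are 3 x 4 for HR and 3 x 2 for bLA and CMJ, with the second factor called measurement times. Study Design places these within a session: rest and end of combat, plus HR after each set.

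**2. Error variance with balanced orders.** Without visit, the expected residual variance is 1 + n × Σ(visit effect - mean)² / (2n - 2). Linear drift gives visit effects -d, 0 and +d, so the sum is 2d² and the variance is 1 + n·d²/(n - 1).

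- d = 0.25: 1 + 12 × 0.0625/11 = 1.07
- d = 0.5: 1 + 12 × 0.25/11 = 1.27
- d = 1: 1 + 12/11 = 2.09

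With visit the variance is 1, and error degrees of freedom fall from 2n - 2 = 22 to 2n - 4 = 20. The ratio of CI widths, with over without visit, is (2.086/2.074)/√variance: 1.006 with no drift, 0.973 at 0.25, 0.892 at 0.5 and 0.696 at 1.

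**3. Simulated power of the condition test, and 95% CI half-width of a pairwise difference.** Both models contain athlete and condition with a pooled error; they differ only in visit.

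| Orders | Drift per visit | Power without / with visit | Half-width without / with visit |
|---|---|---|---|
| Balanced | 0 | 69% / 68% | 0.84 / 0.84 |
| Balanced | 0.25 SD | 66% / 68% | 0.86 / 0.84 |
| Balanced | 0.5 SD | 57% / 68% | 0.95 / 0.84 |
| Simple randomisation | 0 | 69% / 64% | 0.84 / 0.88 |
| Simple randomisation | 0.25 SD | 66% / 64% | 0.86 / 0.88 |
| Simple randomisation | 0.5 SD | 59% / 64% | 0.93 / 0.88 |

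With balanced orders at 0.5 SD, the loss shrinks as n grows: 80% vs 88% at n = 18 and 92% vs 96% at n = 24. Under simple randomisation at n = 12 the term breaks even at about 0.3 to 0.35 SD per visit.

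**4. Type I error without visit.** Balanced orders: 4.8% with no drift, 4.3% at 0.25 SD and 2.5% at 0.5 SD, so the test is conservative. Simple randomisation: about 5% throughout.

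**5. Shift in one allocation.** Under simple randomisation the visit difference between two conditions is -2, -1, 1 or 2 with probabilities 1/6, 1/3, 1/3 and 1/6. Its mean is 0 and its variance is 4 × 2/6 + 1 × 2/3 = 2. Over 12 athletes at d = 0.5, the shift of a contrast has mean 0 and SD 0.5 × √(2/12) = 0.20. It is at least 0.17 SD in 48% of allocations. The contrast's standard error without drift is √(2/12) = 0.41, so 0.17 SD is about 0.4 standard errors.

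**6. What cancels.** A shift common to all measurements of a session drops out of intervention x time. Only drift in the response to combat would remain there.

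**7. PMS read as independent groups.** The error variance becomes within- plus between-athlete variance. At a between-athlete SD of 1 that is 1 + 1 = 2 instead of 1. With no drift, power is about 34%, against about 69% with athlete as a block, and type I error falls below 1%. At between-athlete SDs of 0.5 and 1.5, power is about 60% and 12%.

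**The case against.** The strongest counter-argument is that the documents do not settle even the sign of the benefit. Under simple randomisation the term loses power and widens intervals unless drift exceeds about 0.3 to 0.35 SD per visit. The large gains need 0.5 SD per visit or more, that is, a full within-athlete SD from the first to the last combat visit. Nothing in the documents supports drift of that size, and the familiarisation visit exists partly to reduce it. This stands, and it is why the point is minor.

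Three further limits also stand. The gain does not reach intervention x time unless the response itself drifts. The plan uses CIs only for subjects' characteristics, so interval width matters only if intervals for condition differences are reported as well. And pooled-error contrasts assume equal variances of the pairwise differences, which separate paired t-tests do not.

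A reader might infer more than the material supports:

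- *That the planned tests are invalid or produce excess false positives.* They do not: type I error is at or below about 5%.
- *That the W:R comparisons are biased.* Over randomisation the shift averages zero; only one realised allocation with unequal orders can be displaced.
- *That the narrowing from raw paired t-tests to the model with visit is all due to visit.* It is not. With no drift and balanced orders the half-widths are 0.88 (raw), 0.84 (pooled without visit) and 0.84 (with visit), so that gain is pure pooling. At 0.5 SD they are 0.99, 0.95 and 0.84.
- *That PMS was certainly to be analysed as independent groups.* The wording permits that reading but does not establish it.

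**Conclusion.** The omission is real and the point is minor: a cheap efficiency improvement to a valid plan. With balanced orders the trade favours including visit (about 1 point of power lost with no drift, about 11 gained at 0.5 SD per visit). With simple randomisation it is closer (4 to 5 points lost with no drift, about 5 gained at 0.5 SD), although adjustment also removes the shift peculiar to the realised allocation. All these figures rest on the assumed n = 12, linear drift and equal variances; which case applies cannot be known from the documents. The benefit is confined to condition main effects and comparisons of levels.

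The PMS question is separate and conditional on wording. If an independent-groups test is meant, leaving out athlete can cost far more than leaving out visit.

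**What to change.** For HR, bLA and CMJ, compare conditions with a model of athlete, condition and visit (2, 3, 4) on one summary per session: the session mean for the main effect, and end minus rest for the response to combat. For bLA and CMJ, end minus rest without visit is already the planned interaction test, so this only adds visit. For HR it covers one component, so keep the planned intervention x time analysis for the pattern over its four times. Take pairwise condition differences from the same model, and state the equal-variance assumption. Report how many athletes followed each order.

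For PMS, state that athlete is a within-subject block, and add visit. Treat RPE the same way if it is analysed; it is measured but has no listed analysis.

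The cost is a change of SAP wording and a re-run, with no new measurements. It requires that the visit of each condition was recorded, which the documents do not state, and that orders varied between athletes. The statistical price is two degrees of freedom (22 to 20 at n = 12), plus some loss of precision when orders are unequal. The section is written in the past tense, so if results have already been seen, label the adjusted analysis as added afterwards.

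### Muscle soreness is rated by the same athletes after all three combats, but its ANOVA is not stated to be repeated-measures; run as written, it uses the wrong error term.

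*Combined protocol and SAP*

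**What the plan says.** The Study Design section describes a cross-over: "This randomized cross-over study measured physiological and perceptual responses of taekwondo athletes following a free combat and combats with different W:R ratios". Each athlete fights three combats (free, 1:2 and 2:1). On the perceptual outcomes it says: "Athletes' rating of perceived exertion (RPE) and perceived muscle soreness (PMS) were measured immediately after each combat". No resting PMS value is mentioned, so PMS consists of three ratings per athlete, one per combat.

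The Statistical Analysis section then names these tests:

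- heart rate, lactate and jump: "Two-way ANOVA with repeated measurements (intervention x time) was used to determine changes in HR", with lactate and jump in the same sentence;
- PMS: "One-way ANOVA was used to determine changes in PMS";
- follow-up between ratios: "In case of significant differences between W:R ratios, paired sample t-test was used";
- follow-up over time: "one-way repeated measures ANOVA was used to determine the difference among measurement times".

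Partial eta squared "was calculated to determine the effect size, using the 0.0099, 0.0588, and 0.1379 considered as small, medium, and large effect sizes".

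**The concern.** PMS is the only outcome whose ANOVA lacks the repeated-measures qualifier. The same paragraph uses the full name of the one-way repeated-measures test for another comparison, so a reader can fairly take the two names as two different tests. Without a qualifier, one-way ANOVA ordinarily means the independent-groups test. Applied to three matched ratings per athlete, that test has two consequences.

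- **Significance test.** Stable differences between athletes in how they rate soreness stay in the denominator of F. If ratings correlate positively within athlete, the test rejects too rarely. A null PMS result could then not be relied on; a significant one would not be made spurious by this.
- **Effect size.** The same sum of squares enters partial eta squared. PMS would be graded on a different base from heart rate, lactate and jump, against the same fixed cut-offs.

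**Working it through.** The documents state no sample size, SD, correlation or PMS result, so there is no figure of the plan's own to reproduce. The check compares the two error terms algebraically and then by simulation.

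**From the documents:** three conditions per athlete, one PMS rating per condition, significance level 0.05, cut-offs 0.0099, 0.0588 and 0.1379.

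**Assumed:** total SD 1; condition means −d, 0, +d; equal within-athlete correlation ρ; n athletes; normal data.

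**Step 1: algebra.** Let SSc be the sum of squares for condition.

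- As written: F = (SSc/2) / (SSwithin/(3n−3)).
- Repeated measures: F = (SSc/2) / (SSerror/(2n−2)), with SSerror = SSwithin − SSathlete.
- Since SSathlete ≥ 0, SSc/(SSc + SSwithin) ≤ SSc/(SSc + SSerror). On any data set the independent-groups partial eta squared cannot exceed the repeated-measures one.

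**Step 2: one case by hand** (n = 12, d = 0.4, ρ = 0.5).

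- Expected mean square for condition: (1−ρ) + n·d² = 0.5 + 12 × 0.16 = 2.42.
- Expected error mean square: ρ + (1−ρ) = 1 as written; 1−ρ = 0.5 for repeated measures.
- Ratio: 2.42/1 = 2.42 against 2.42/0.5 = 4.84.
- 5% critical values: 3.28 on (2, 33) df and 3.44 on (2, 22) df.

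The typical F lies below its threshold in the first test and above it in the second.

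**Step 3: simulation** (60,000 trials per setting; repeated measures with the Greenhouse-Geisser correction). Power at d = 0.4, as written vs repeated measures:

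| n | ρ = 0.1 | ρ = 0.3 | ρ = 0.5 | ρ = 0.7 |
|---|---|---|---|---|
| 8 | 23 vs 21% | 19 vs 27% | 16 vs 37% | 13 vs 59% |
| 12 | 36 vs 36% | 32 vs 45% | 28 vs 60% | 24 vs 83% |
| 20 | 59 vs 61% | 58 vs 72% | 57 vs 87% | 56 vs 98% |

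At n = 12, the true type I error of the test as written is about 3.7, 1.6, 0.5 and 0.1% at ρ = 0.1, 0.3, 0.5 and 0.7, against a nominal 5%. At d = 0.8 and n = 20 both tests exceed 99% power.

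Median partial eta squared at n = 12, ρ = 0.5:

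| d | As written | Repeated measures |
|---|---|---|
| 0.2 | 0.04 (small) | 0.12 (medium) |
| 0.4 | 0.12 (medium) | 0.29 (large) |
| 0.8 | 0.33 (large) | 0.60 (large) |

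**Step 4: sensitivity.** Rounding and clipping the ratings to an assumed 0–10 scale (n = 12, d = 0.4, ρ = 0.3/0.5/0.7) gives 32/28/24% vs 44/58/80%, so the contrast does not depend on continuous data. With unequal pairwise correlations of 0.8, 0.3 and 0.3 at n = 12, type I error is 6.6% for repeated measures uncorrected and 4.8% with Greenhouse-Geisser; power at d = 0.4 is 29% as written against 49% corrected.

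**The case against.** The best reply is that only the wording is at fault. The plan never calls the PMS test independent or unpaired. PMS has one value per combat, so the only contrast it offers is between ratios, and the stated follow-up for that contrast is a paired t-test. The authors evidently knew the data were paired. This is plausible and cannot be excluded. It does not clear the text: if the label is shorthand, the test is misnamed and cannot be reproduced from the description; if it is literal, the omnibus test does not match its own follow-up.

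Three further points stand as limits.

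- The harm is one-sided and depends on correlation. At ρ = 0 the test as written is slightly the more powerful (n = 12, d = 0.4: 37% vs 32%), and at n = 8, ρ = 0.1 it is still level or ahead. The Greenhouse-Geisser correction is itself somewhat conservative in samples this small.
- A different effect-size grade is not always an error of the independent-groups value. With no true effect at n = 12, the repeated-measures median is about 0.06, already above the 0.0588 cut-off, through small-sample upward bias. What survives is comparability: PMS should be graded on the same kind of error term as the other outcomes.
- PMS is one of five measures and no primary outcome is named.

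**Conclusion.** The point holds. As written, the PMS test and its partial eta squared ignore the matching that the cross-over creates. The ordering of the two partial eta squared values is algebraic and needs no assumption; the loss of significance level and power requires positive within-athlete correlation. At an assumed n = 12 and d = 0.4, the power deficit is 45 − 32 = 13 points at ρ = 0.3, 60 − 28 = 32 at ρ = 0.5 and 83 − 24 = 59 at ρ = 0.7; it is nil at ρ = 0.1. The consequence is confined to the PMS conclusion and its effect-size label. Whether the analysis or only its description is wrong cannot be told from the documents, so confidence that results are affected is moderate. It should be fixed.

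**What to change.** Replace the PMS sentence with one of this kind: PMS was compared across the three combats by one-way repeated-measures ANOVA with combat condition as the within-subject factor, partial eta squared was taken from the same model, and paired comparisons followed. A Greenhouse-Geisser correction is advisable with three conditions; whichever choice is made about sphericity should be stated.

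- If PMS was already analysed this way, only the wording changes.
- If an independent-groups test was run, re-run PMS and its partial eta squared on the ratings in hand.
- If a Friedman test is preferred because the ratings are ordinal, justify it by the nature of the scale, not by the outcome of a normality test.

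A separate reporting gap can be closed in the same edit: perceived exertion is also rated after each combat, but the Statistical Analysis section names no test for it. State which within-athlete test was used.

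The cost is a sentence or two and at most a short re-analysis with standard procedures in SPSS or JASP, which the plan already uses. No new measurements are needed.

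### Pairwise Cohen's d between combat formats is produced and graded only after a significant difference, so the reported values and their size labels are biased upwards by an amount the documents do not fix

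*Combined protocol and SAP*

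**What the plan says.** The Study Design section describes a randomised cross-over in which each athlete fights in three formats: free, 1:2 and 2:1. That gives three pairwise contrasts per outcome.

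The Statistical Analysis section first fits two-way repeated-measures ANOVAs (3 x 4 for heart rate, 3 x 2 for lactate and for jump) and a one-way ANOVA for muscle soreness. The follow-up between formats is conditional: "In case of significant differences between W:R ratios, paired sample t-test was used". The pairwise effect size belongs to that follow-up. The sentence opens "Cohen's d for paired sample t-test was" and continues "automatically provided by JASP software and classified as 0.2 (small), 0.5 (medium) and 0.8 (large"). The threshold is 5%: "Statistical significance was set at" p < 0.05.

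Two other statements bear on the point. Partial eta squared "was calculated to determine the effect size, using the 0.0099, 0.0588, and 0.1379 considered as small, medium, and large effect sizes", with no significance condition. The only confidence intervals mentioned are for the athletes' characteristics: "Descriptive statistics and 95% confidence intervals (CI) were used to present subjects' characteristics". No sample size, power or expected effect is given.

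**The concern.** An estimate that appears only when the data have crossed a significance threshold is too large on average, because the trials (or outcomes) in which chance pulled the difference towards zero are filtered out. The plan then grades the surviving d, so the label moves up with the estimate.

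This matters because the practical question is how far free, 1:2 and 2:1 combat differ. The pairwise differences answer it. Partial eta squared is an omnibus quantity: it has no direction, does not say which formats differ, and is not in units of heart rate, lactate or jump performance. Adding a confidence interval behind the same gate would not repair the problem, since that interval is selected too.

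**Working it through.** There is no figure in the plan to reproduce, so the check asks how much bias the stated rule produces under declared assumptions.

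**Inputs from the documents.** Three within-athlete formats; test level 0.05 (taken as two-sided); d graded at 0.2, 0.5 and 0.8; pairwise d only after a significant format difference.

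**Assumptions.** n = 12 to 20 athletes as the main range, with 8 to 40 also examined. Normal data. d = mean paired difference / SD of the paired differences. A one-way format effect, which for the 3 x 2 outcomes is the same as the format-by-time interaction on change from rest. Free combat midway between the two ratios.

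**Model.** Independent residuals with SD 1, so the SD of a difference is √2. The two ratios are shifted by ± d√2/2. For d = 0.5 each shift is 0.354, the mean difference is 0.707, and 0.707/1.414 = 0.5. The gate is the repeated-measures F test at 5%. Between 40,000 and 100,000 trials were simulated per setting. Repeat runs agreed to about 0.01 in mean d and about one percentage point in the shares.

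**Results for 2:1 against 1:2:**

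| True d | n | Reported in | Mean d, all trials | Mean d, gated | Raw difference inflated | Graded large, all trials | Graded large, gated |
|---|---|---|---|---|---|---|---|
| 0.3 | 12 | 13% | 0.32 | 0.77 | 2.2-fold | 7% | about 48% |
| 0.3 | 20 | 19% | 0.31 | 0.62 | 1.9-fold | 3% | 14% |
| 0.5 | 12 | 28% | 0.54 | 0.90 | 1.6-fold | 20% | 62% |
| 0.5 | 20 | 47% | 0.52 | 0.72 | 1.3-fold | 13% | 28% |
| 0.8 | 12 | 63% | 0.86 | 1.05 | 1.19-fold | 52% | 79% |
| 0.8 | 20 | 88% | 0.83 | 0.89 | 1.06-fold | 52% | 59% |

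The small excess in the ungated means is the ordinary small-sample bias of d. Multiplying by 1 − 3/(4(n − 1) − 1) removes it: at n = 12 the factor is 1 − 3/43 = 0.93, and 0.54 × 0.93 = 0.50.

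**Label shift.** For a true d of 0.3, gated results are graded medium or higher in about 87% (n = 12), 80% (n = 20) and 55% (n = 30) of cases, against about 27%, 21% and 16% without the gate.

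**Why large depends on n.** The smallest |d| that a paired t-test can declare significant is t(0.975, n − 1)/√n: 0.84 at n = 8, 0.64 at n = 12 (2.201/3.464) and 0.47 at n = 20 (2.093/4.472). So a significant pair must be large only at about n = 8. At n = 16 to 24 the commonest label for a small-to-medium effect is medium.

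**Other mean pattern.** If one format differs and the other two are equal, a true d of 0.5 is graded large, when gated, in 49% of cases at n = 12 and 22% at n = 20.

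**Interval behind the gate.** For a true d of 0.3, a 95% interval reported only after a significant ANOVA covers about 79% at n = 12 and 87% at n = 20.

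**The case against.** Testing an omnibus effect first and pairs afterwards is conventional, and no false-positive problem is alleged here. That is right, and the point is confined to estimation.

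A reader might infer that small-to-medium effects will generally be called large. The documents do not support this. They give no sample size, and in the model above large is the majority label only near n = 12 or below, with free combat midway.

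A reader might also infer that all the trial's effect sizes are selected, or that non-significant outcomes yield no estimate at all. Neither follows. Partial eta squared is calculated and graded without a gate. The quoted sentence is a testing sequence and does not say that format means are withheld. The section is silent on tabulated means, and silence is not a rule.

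The strongest objection is that the one-way model is not the planned analysis. The text does not say whether the format main effect or the interaction is the trigger, or at which time point the paired test is made. Take a true d of 0.5 at the end of combat and assume a rest-to-end correlation of 0.6. An interaction trigger then gives raw inflation of only 1.23-fold (n = 12) and 1.13-fold (n = 20), with large in 31% and 18%. A main-effect trigger goes the other way, with large in about 68% and 50%. The 3 x 4 heart-rate analysis, period effects and departures from sphericity were not simulated. This objection stands against any single figure for the bias. It does not change the direction, which was upwards in every case with a true effect examined.

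**Conclusion.** The concern holds for the pairwise Cohen's d. On the plain reading of the Statistical Analysis section these values arise only after a significant format difference, so they are biased upwards and their labels are shifted up. The figures of 0.6 to 0.9 for a true d of 0.3 to 0.5, and raw inflation of 1.3- to 2.2-fold, are conditional on n = 12 to 20, a one-way format effect and free combat midway. They illustrate the size and are not predictions for this trial. The bias fades as power rises and is small at a true d of 0.8 across that range of n. This is a defect of reporting that should be corrected; it does not invalidate the significance tests.

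**What to change.** For each outcome, report the paired mean difference and d, each with a 95% confidence interval, for all three format pairs, whatever the ANOVA result. Use end-of-combat values or change from rest (muscle soreness is measured only after combat). Keep the ANOVA as the gate for significance claims only, and say that these intervals are descriptive. Attach the small, medium and large labels to the ungated estimates, optionally after the small-sample correction to d. Ungated estimates no longer depend on which ANOVA term was the trigger.

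The cost is a sentence or two in the analysis section and a longer results table. One contrast for each of the four outcomes with a named analysis gives 3 x 4 = 12 rows. Every time point would give 3 x (4 + 2 + 2 + 1) = 27 rows, including comparisons at rest that add little. No new data are needed, no significance claims are added, and error rates do not change.
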